## **4.0 SAFETY MONITORING**

### **4.1 Safety population**

The safety population will consist of all study accrued patients, including those on research exclusions lists. Like the ITT population, patients will be assigned to the clinic at which their index visit took place, and to the treatment arm to which their clinic was randomized.

### **4.2 Safety events**

Safety events will be monitored via passive surveillance of EHR and administrative data sources maintained by the health system, and state mortality data, for all safety population patients. Benefits to this approach are that safety events can be ascertained identically for all accrued patients in all randomized clinics. Documentation will occur while delivering health care or administering health insurance so that records should be reasonably accurate and complete with minimal and randomly missing information. When care for safety events is delivered outside the care system, health care claims can document their occurrence for patients who are also health plan members. Missing information due to events for which patients do not seek care or care that escapes documentation in the EHR or claims will be assumed to occur equally across treatment groups.

We will monitor emergency department (ED) visits, hospitalizations, suicide attempts, and deaths as safety events among all accrued patients from one year prior to their index visit through the end of the observation period. ED and hospital encounter dates, and suicide attempt and self-harm diagnosis code dates, will be used to determine whether safety events occurred pre- (365 to 1 days prior to index) or post-index (on the index visit date through the lesser of date of death or observation period end).

### **4.3 Safety reporting**

A report will be prepared by the study statisticians and provided to the Data Safety Monitoring Board (DSMB) at a frequency determined by the DSMB. The report will provide information regarding patient accrual, intervention delivery and safety events. Patient accrual will be tracked through monthly and cumulative counts of actual and expected counts of index visits. Pre-randomization clinic characteristics and patient characteristics as of index visit date will be provided overall and by treatment group. CI-CDS use will be tracked monthly and cumulatively by treatment arm to monitor intervention adherence (intervention clinics) and check for contamination (control clinics).

The following metrics will be calculated for each safety event: total number of events, allowing multiple per patient; proportion of accrued patients with at least one event; and event rate in patient-years. Each of these metrics will be compared across treatment arms and two time periods (post-index vs. 1 year pre-index). Data from the pre-index year will provide baseline information about the prevalence of each safety event prior to potential CI-CDS intervention exposure. Post- and pre-index rates will be compared to identify differential changes in safety event rates.

As safety events will be summarized by treatment arm using EHR and administrative data, it is not feasible to assess relationship to the study intervention, *per se*. Instead, the study team and DSMB will evaluate safety data at an interval determined by the DSMB to evaluate differences in safety event rates across treatment arms.

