7.3.2 Safety events

Adverse Event (AE):

As this is a minimal risk study, with the CI-CDS intervention layered on top of usual care, adverse events will not be collected in the context of this trial.

Safety Events:

- emergency department visits
- hospitalizations
- suicide attempts
- death

We will extract data from the EHR and administrative databases to monitor safety events that occurred from 1 year prior to each accrued patient's index visit date through the end of the observation period. The following activities will be carried out at a frequency determined by the DSMB. The study statistician will assemble the random, unique study identifier and index visit date for all accrued patients. A study programmer will extract data elements needed to characterize the patient sample and to quantify rates of emergency department visits, hospitalizations, suicide attempts, and deaths. State preliminary manner of death data are sent to HealthPartners monthly, with a lag of about a month; these data and final adjudicated cause of death data are incorporated into HealthPartners databases upon receipt. The statistician will assemble a safety report and provide it to the co-PIs, OCHIN Lead Co-Investigator and the DSMB.

The DSMB report will provide information regarding patient accrual, intervention delivery and safety events. Patient accrual will be tracked through monthly and cumulative counts of actual and expected counts of index visits. Pre-randomization clinic characteristics and index visit date patient characteristics will be provided overall and by treatment group within site. CI-CDS use will be tracked monthly and cumulatively by treatment arm within site to monitor intervention adherence (intervention clinics) and check for contamination (control clinics).

The following metrics will be calculated for each safety event: total number of events (allowing multiple per patient), proportion of accrued patients with at least one event, and the event rate in patient-years. Each metric for each event will be compared between the treatment groups (intervention vs. control) and over time (post-index vs. 1 year pre-index). Data from the year prior to each patient's index visit will provide baseline data regarding the prevalence of each safety event. Post-index data will be compared to baseline data by treatment group to identify differential changes in safety event rates.

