## **2.0 STUDY DESIGN AND PROCEDURES**

### **2.1 Study Design Overview**

This large, unblinded, clinic-randomized pragmatic trial will evaluate the effectiveness of the CI-CDS system in improving care for patients with elevated risk for CI by making it easier for primary care clinicians to assess, diagnose, and manage individuals with CI. The study will be conducted in at least 30 HealthPartners primary care clinics, where at least 3000 patients with elevated risk for CI are estimated to receive care.

The CI-CDS software is a system level intervention comprised of 1) a passively operating web service that gathers, analyzes and retains information pertinent to every web service call, and 2) a user interface that presents a summary of algorithm results to front end users. The web service documents every web service call made by all front-end users in all participating locations so that data pertinent to all targeted visits from all eligible and accrued patients will be identically collected and available in both treatment arms. The user interface will function as the intervention delivery vehicle and therefore be operative only in intervention locations.

Clinics will be randomized equally to the CI-CDS or UC treatment group using simple randomization. CI-CDS clinics will fully implement the CI-CDS system. In these clinics, the CI-CDS will identify patients who are at high risk for CI; use data stored in the EHR for these patients to assemble treatment recommendations tailored to the current needs of each patient; display these recommendations via the CI-CDS user interface; and store analytic data from all targeted visits. UC clinics will silently implement the CI-CDS system at the same time as CI-CDS clinics so that it operates undetectably in the background. In these clinics, the CI-CDS will identify patients at high risk for CI, assemble treatment recommendations and store analytic data from all targeted visits.

The 12-month patient accrual period will begin at the same calendar time in all clinics when the CI-CDS system is implemented. The up to 24-month intervention period will begin in all clinics at the same time as the accrual period and is the time during which the CI-CDS interface will be operative in intervention clinics.

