Each patient will accrue into the study at their index visit. The index visit is the first visit during the accrual period at a randomized clinic at which a patient meets all intervention eligibility criteria. The index visit date will mark the beginning of each accrued patient's observation period. Patients will have up to 24 months of observation period, and those with an index visit near the end of the accrual period will have an approximate 12-month observation period.

Following intent-to-treat (ITT) principles, all accrued patients will be attributed to the clinic at which their index visit took place, and to the treatment group to which their clinic is randomly assigned. Patients who have an index visit, and thus have accrued into the study, may have additional visits at randomized clinics prior to the end of the intervention period. The CI-CDS system is programmed to assess intervention eligibility at all visits at all randomized clinics in both treatment groups for the duration of the intervention period, and to display tailored CI-CDS for eligible post-index visits in CI-CDS clinics only.

[figure not shown]
In addition to the primary effectiveness trial, the CI-CDS system will be implemented and evaluated in a separate, independent health care system. The replication site study design will be similar in that up to 30 primary care clinics will be randomized to a CI-CDS or UC treatment group. The CI-CDS system will be fully implemented in CI-CDS clinics and partially implemented in UC clinics (i.e., working in the background to collect data but not visible to clinicians). Patients will accrue into the study at index visits over a 6-month accrual period, with an approximate 6-month observation period for the last accrued patient, resulting in a ~12-month intervention period.

Structural differences between the effectiveness and replication sites require that processes such as randomization, outcome measurement, and analysis be implemented differently at the replication relative to the effectiveness site. Information about these processes at the replication site will be provided in a site-specific supplemental analysis plan.

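### Safety counts and proportions are compared pre- versus post-index over windows of unequal length, and for deaths that comparison carries no information

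*SAP*

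**What the plan says.** SAP 4.2 sets the two windows. The first is fixed: "pre- (365 to 1 days prior to index" days. The second is open-ended: "post-index (on the index visit date through the lesser of date of death or observation period end". Neither document caps it at 365 days.

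SAP 4.3 names the metrics: "total number of events, allowing multiple per patient; proportion of accrued patients with at least one event; and event rate in patient-years". It then gives the comparison rule: "Each of these metrics will be compared across treatment arms and two time periods (post-index vs. 1 year pre-index". Protocol 7.3.2 has the same rule: "Each metric for each event will be compared between the treatment groups (intervention vs. control) and over time (post-index vs. 1 year pre-index". The listed events are emergency department visits, hospitalisations, suicide attempts and deaths.

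SAP 4.3 also states a purpose in terms of rates: "Post- and pre-index rates will be compared to identify differential changes in safety event rates".

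Follow-up is set in SAP 2.1: "The 12-month patient accrual period will begin at the same calendar time in all clinics when the CI-CDS system is implemented", and "Patients will have up to 24 months of observation period", with about 12 months for those accrued last. SAP 4.3 leaves the timing of safety reports to the DSMB, so a report may fall at any point in follow-up.

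**The concern.** Of the three metrics, only the patient-year rate allows for the length of observation. A count or a proportion over one year cannot be set against a count or a proportion over three months or eighteen months without building in a difference that has nothing to do with the intervention. While mean follow-up is under a year, the table shows a fall in events. Once it passes a year, the table shows a rise.

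Death is a separate problem. A patient must be alive at the index visit to be accrued, so the pre-index period contains no deaths whatever metric is used.

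At stake is how a table prepared for safety monitoring is read. No primary or secondary outcome is involved.

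**Working it through.** **Inputs from the documents.** Pre-index window 365 days (SAP 4.2). Accrual over 12 months from a common start, and an intervention period of up to 24 months (SAP 2.1).

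**Assumptions.** A constant event rate λ, the same before and after index (no true change); uniform accrual; time after death ignored at first. The documents give no event rates, so 0.05 to 1.0 events per patient-year is used as a range.

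**1. The plan's own follow-up range.** 24 months minus an index month of 0 to 12 gives 24 down to 12 months, which agrees with SAP 2.1. The mean under uniform accrual is 24 − 6 = 18 months.

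**2. Counts.** Expected pre-index events per patient are λ × 1. Expected post-index events are λ × mean T, where T is follow-up in years at the report date. The ratio is mean T, whatever λ is.

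**3. Proportions.** Pre-index: 1 − e^(−λ). Post-index, with T uniform on [a, b]: 1 − (e^(−λa) − e^(−λb)) / (λ(b − a)). At λ = 0.4 the pre-index value is 1 − 0.6703 = 33.0%. At month 24 (a = 1, b = 2) the post-index value is 1 − (0.67032 − 0.44933)/0.4 = 1 − 0.55248 = 44.8%.

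| Report month | T (years) | Count ratio post/pre | Post-index proportion, λ = 0.4 (pre 33.0%) | Proportion ratio |
|---|---|---|---|---|
| 6 | 0 to 0.5 | 0.25 | 9.4% | 0.28 |
| 12 | 0 to 1.0 | 0.50 | 17.6% | 0.53 |
| 18 | 0.5 to 1.5 | 1.00 | 32.5% | 0.99 |
| 24 | 1.0 to 2.0 | 1.50 | 44.8% | 1.36 |

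**4. Sensitivity.**
- Across λ from 0.05 to 1.0, the proportion ratio is 0.25 to 0.34 at month 6, 0.50 to 0.58 at month 12 and 1.21 to 1.48 at month 24.
- With front- or back-loaded accrual instead of uniform, the change from apparent fall to apparent rise in counts moves from month 18 to between 16.5 and 19.2.
- Ending person-time at death, with assumed mortality of 3 to 10% per year, leaves the month-24 count ratio at 1.39 to 1.47.

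**5. Patient-year rate.** Events divided by person-time give λ in both windows, so the post/pre ratio is 1.00 at every report date.

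**6. Deaths.** Pre-index count, proportion and rate are all zero by design, so no post/pre contrast is informative. The SAP 4.2 sentence that assigns events to pre or post names emergency department and hospital encounter dates and suicide attempt or self-harm code dates. It does not say how deaths are assigned, while SAP 4.3 and protocol 7.3.2 apply the pre/post rule to every event.

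**7. Between arms.** Both arms have the same mean T if accrual timing is similar, so the ratio of the two post/pre count ratios is 1. A difference of differences in raw counts does not cancel if baseline rates differ. With 1500 patients per arm (half of the planned 3000), assumed rates of 0.6 and 0.5 and no effect, it is 1500 × 0.1 × (0.50 − 1) = −75 events at month 12 and 1500 × 0.1 × (1.50 − 1) = +75 at month 24.

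**8. Replication site.** Accrual over 6 months with about 6 to 12 months of observation gives a final count ratio of about 0.75, so only an apparent fall could arise. It would concern only suicide attempts, the one event monitored there (protocol 15.5, section 7.3.2). The SAP defers that site to a supplemental plan.

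**The case against.** The strongest reply is that the plan already holds the right measure and points to it. The patient-year rate is one of the three metrics, and SAP 4.3 frames the pre/post comparison in terms of rates. Protocol 9.3 ties any suspension of accrual or change in delivery to differing event rates by treatment group, not to a within-arm change in counts. Both arms share one accrual calendar. The baseline column is labelled as one year, accrual counts appear in the same report, and the DSMB also receives clinician feedback (protocol 7.3.1). An experienced board is unlikely to take a small count after brief follow-up as a safety gain, and a row of zero pre-index deaths explains itself.

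Most of this stands, and it limits the weight of the point. A reader might infer that the DSMB's safety evidence as a whole is unsound, or that early reports will falsely reassure it. The documents do not support that: the rate and the between-arm contrasts remain usable, very early reports are possible but not certain, and no decision rule rests on the affected comparison. Nor does the plan prescribe a difference of differences in raw counts; step 7 shows only what would follow if the stated interest in differential change were pursued on that scale.

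The reply does not remove the instruction itself. The sentence just before the one on rates orders all three metrics to be compared across the two periods, and protocol 7.3.2 repeats this for each event.

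**Conclusion.** The point holds, confined to the pre/post comparison of counts and proportions, and to any pre/post comparison of deaths. With no true change, counts appear to fall by 75% at month 6 and to rise by 50% at month 24, and proportions move in the same direction. The count ratios rest on a constant rate and uniform accrual, and do not depend on the event rate. The proportions rest on assumed rates, since the documents give none, and an assumption such as 0.4 per year does not suit a rare event like a suicide attempt. The death point needs no assumption.

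Even the within-arm patient-year contrast calls for care, because patients must survive to index and MC-PLUS uses past utilisation to select them. The between-arm difference in rates is the sounder evidence. This is a clear error in a stated rule, cheap to correct and modest in consequence.

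**What to change.** In SAP 4.3 and protocol 7.3.2:

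- Restrict pre/post comparisons, and any comparison of differential change, to patient-year rates, with person-time ending at death or the data cut for the report.
- Show counts and proportions between arms only, with patient and person-time denominators. Simple randomisation of clinics does not ensure equal patient numbers per arm.
- Report deaths between arms only.
- If a pre/post proportion is wanted, use windows of equal length. A 365-day post-index proportion is not available until patients have reached 12 months, so it cannot serve reports before then.

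The cost is a few sentences in each document and a small change to the table programs. No new data are needed.

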## 5.0 DATA QUALITY AND MISSINGNESS

### 5.1 Person-based missingness

Patients whose data will be used for the primary and secondary effectiveness analyses will not be consented and are unlikely to be aware that their data are being used for this research. Only patients who have requested that their data not be used for research and appear on opt out lists will be excluded. Very few patients have made such a request. For these reasons we expect person-based missingness to be extremely rare.

### 5.2 Event-based missingness

Outcomes that assess clinical effectiveness, cost, utilization and safety will be calculated using data extracted from EHR and administrative data sources maintained by HealthPartners. As such, these outcomes will be ascertained identically for all accrued patients in all randomized clinics. Documentation of these outcomes will have occurred in the course of delivering health care (clinical, utilization outcomes) or administering health insurance (cost outcomes) so that records should be reasonably accurate and complete with minimal and randomly missing information. The absence of documentation of an event is virtually always due to it not having taken place. Truly missing field-based observations (e.g., CI diagnosis assigned, documentation not found) will be extremely rare, undetectable and assumed to occur at random. When care is delivered outside the HealthPartners care system, health care claims can document their occurrence for patients who are also HealthPartners insurance members. Missing information due to events for which patients do not seek care or care that escapes documentation in the EHR or claims will be assumed to occur equally across treatment groups. The estimation techniques used in the planned random coefficient models readily accommodate structural variation across observations in the amount of data present (e.g., patients per clinic) and lead to unbiased parameter estimates and accurate standard errors when data are missing at random.

### 5.3 Data security and quality

The CI-CDS itself will house the algorithms, communicate with and display within the EHR, and store data required to assess study objectives in a secure analytic database at HealthPartners Institute. These data, supplemented by EPIC Clarity and administrative claims data, will be used to assess CI-CDS use rates, diagnosis of CI, and hospitalizations and emergency department visits. Data collected from the primary care clinicians via surveys will be similarly housed on secure servers at HealthPartners Institute.

As this study is conducted as a pragmatic clinical trial, with CI-CDS being suggested to primary care clinicians in the course of usual care, the training and quality control metrics typically found in traditional randomized trials do not apply. Primary care clinicians will receive training on use of the CI-CDS, and print rates will be monitored and communicated to clinicians, as noted above.

## 6.0 SAMPLE SIZE AND POWER

The primary hypothesis test will compare patients in CI-CDS clinics to those in UC clinics on the likelihood that CI is diagnosed during the observation period. We conducted a power analysis to estimate the minimum detectable rate of new CI diagnoses given ranges of assumptions about

analytic sample sizes, proportions of patients currently meeting outcome criteria, and clinic intraclass correlation ( $ICC_{clin}$ ).

We used data accrued into the CI-CDS system during the R61 silent pilot to identify patients who met intervention eligibility criteria at clinic visits (section 2.3.3). Based on the pilot CI-CDS data, we estimated that, on average, about  $n=100$  patients in each of at least 30 clinics will likely have an index visit over the course of a 12-month accrual period.

An EHR-based cohort that consisted of patients who were age  $\geq 65$  and had a primary care visit between September 2021 and August 2022 was assembled to provide estimates of CI diagnosis rates in primary care clinics that were candidates for randomization. The proportion of patients who had at least one CI diagnosis code at an encounter or listed on their active problem list during the 12-month period was 2.3% among all patients in the cohort, and 15.1% among those who had a MiniCog $<3$  during the period. The power analysis will assume that 8-

16% of study accrued patients in UC clinics will have CI recognized between their index visit and end of their observation period.

There was substantial variation across primary care clinics in the proportion of patients with CI recognized as an encounter diagnosis or on their active problem list at the time of their 2021-2022 primary care visit. Among all patients,  $ICC_{clin}=0.03$ , and among those with MiniCog $<3$ ,  $ICC_{clin}=0.04$ . The power analysis will assume  $ICC_{clin}=0.03-0.05$ .

Based on these data-informed estimates, we used the following assumptions regarding the primary effectiveness study for the power analysis: 30, 34 or 38 clinics randomly assigned 1:1 to CI-CDS or UC,  $n=100$  patients per clinic,  $ICC_{clin}=(0.03, 0.04, 0.05)$  and diagnosis rates = (8%, 12%, 16%) in UC clinics. The correlated sample size estimate,  $N$ , was divided by the design effect ( $deff$ ;  $1+(n-1)*ICC$ ) to estimate an effective independent patient sample size (i.e.,  $N_{eff}=N/deff$ ). The power analysis (power=0.80,  $\alpha_2=0.05$ ) estimated the minimum detectable CI-CDS CI diagnosis rate from a single binary predictor in a logistic regression model using the downwardly adjusted effective sample size.

Given the median assumptions for number of randomized clinics,  $ICC_{clin}$  and CI diagnosis rate, the study is powered to detect a diagnosis rate of 19.8% in CI-CDS clinics relative to 12% in UC clinics (Table 1). The absolute increase in diagnosis rates ranges from 5.6% (38 clinics,  $ICC_{clin}=0.03, 8\%$ ) to 10.2% (30 clinics,  $ICC_{clin}=0.05, 16\%$ ) across the range of these assumptions.

**Table 1.** Minimum detectable rates of CI diagnosis in CI-CDS clinics assuming  $n=100$  accrued patients per clinic, 30-38 clinics,  $ICC_{clin} = 0.03-0.05$  and UC diagnosis rates = 8-16%.

		UC diagnoses (%)		
clinics	$ICC_{clin}$	8%	12%	16%
30	0.03	14.4	19.4	24.2
	0.04	15.3	20.4	25.2
	0.05	16.1	21.3	26.2
34	0.03	14.0	18.9	23.6
	0.04	14.8	19.8	24.6
	0.05	15.5	20.6	25.5
38	0.03	13.6	18.5	23.2
	0.04	14.4	19.4	24.1
	0.05	15.1	20.1	24.9

